3.1 Hypotheses

For the first primary study objective (overall assessment of efficacy), the following hypotheses will be tested for each intervention (independently of the other interventions):

1. Intervention A does not improve FEV₁ percent predicted compared to placebo (the null hypothesis) versus A is better than placebo (the alternative hypothesis)
2. Intervention A does not improve asthma symptom control assessed via ACQ-6 compared to placebo (the null hypothesis) versus A is better than placebo (the alternative hypothesis)

The second primary objective involves estimation of the optimal subgroup for targeting participants for each intervention. No formal statistical hypotheses will be tested for this objective.

3.2 Primary and Key Secondary Efficacy Assessments

Primary Efficacy Assessments: Efficacy of each intervention will be evaluated with respect to lung function and asthma symptom control. Lung function will be measured prior to and post bronchodilator administration (pre-BD and post-BD). The American Thoracic Society (ATS) criteria for assessing lung function will be applied for spirometric maneuvers. A central spirometry reading center will provide quality control over-reads of the measurements and identify any issues requiring retraining of clinical staff. The primary efficacy outcome with respect to lung function is FEV₁ percent predicted pre-BD, measured in the clinic. In the event of a clinic shut-down, home spirometry assessment of the primary endpoint will be used.

Asthma symptom control will be measured using six items from the Juniper Asthma Control Questionnaire (ACQ-6) corresponding to five self-reported symptoms and self-reported rescue BD use. The primary efficacy outcome with respect to asthma control symptoms is the average score of these six items (range 0-6).

Secondary Efficacy Assessments: The use of CompEx events as a key secondary endpoint provides an outcome with statistical properties that approximate exacerbations but with a shorter follow-up time.² CompEx is a composite outcome specific to asthma that combines clinically relevant deteriorations captured by diary events with exacerbations, thereby providing an increase in power compared to using exacerbations alone. Exacerbations will be analyzed as another secondary efficacy endpoint.

CompEx events include exacerbations and deterioration events defined based on

- 1) Daily recordings of peak expiratory flow (PEF) morning/evening (L/min)
- 2) Reliever use morning/evening (doses)
- 3) Symptoms morning/evening (score 0–3) assessed from twice-daily diary recordings

The diary event can occur as defined by threshold and slope criteria within a moving window of 5-day length. Evening and morning recordings are treated as separate variables. The baseline levels of deterioration are calculated for each individual as the mean over the 5-10 days ending just before the day of randomization for each of the diary variables. No imputation of missing diary data after the randomization is performed. Deterioration criteria is assessed for each (single) diary variable for thresholds and slopes as follows:

Thresholds: The change from baseline is calculated. If two consecutive days fulfil the chosen threshold limit as defined in Table 3, the deterioration criterion is met.

Slopes: A slope is calculated via univariate linear regression over 5 days. If the slope fulfills the chosen cut-point as defined in Table 3, the deterioration criterion is met.

Diary event start definition: A diary event can occur when (i) the threshold deterioration criterion is met for at least two diary variables, or when (ii) the threshold deterioration criterion is met for one diary variable, and the slope criterion is fulfilled for all included variables. In case of (i), the diary event is defined to start on the first day of the two consecutive deterioration days (event days 0–1). Any missing data in this two-day window will make the event missing. In case of (ii), the event is defined to start on the first of the two days fulfilling the threshold criterion. This means that the slopes are calculated for days -4 to 0 of an event. At least two days with data are needed to calculate slopes in order to qualify as an event. The end of a diary event is the last day that the criteria for a diary event is fulfilled. In order to be counted as a new diary event it must be preceded by at least 7 days in which neither criterion for a diary event is fulfilled.

Table 3. CompEx Threshold and Slope Values

Diary variable	PEF (P) morning/evening	Reliever use (R) morning/evening	Symptoms (S) morning/evening
Threshold type	Decrease from baseline (%)	Increase from baseline (doses)	Increase from baseline (scores) or absolute maximum score
Threshold	15	1.5	1
Slope type	Decrease rate (% per day)	Increase rate (doses per day)	Increase rate (scores per day)
Slope	3	0.3	0.2

3.3 Other Secondary Efficacy Assessments

1. FEV₁, post-BD
2. FVC, pre-BD
3. Exacerbations, time to first (see Section 3.5.3 below)
4. Symptom Free days (defined using diary/CompEx data), where a symptom free day is defined as a symptom score = 0 for both morning and evening in the daily diary
5. Healthcare utilization
 - a. Asthma-specific ED visits
 - b. Asthma-specific hospital admissions
 - c. Asthma-specific Intensive Care Unit (ICU) admissions
6. Asthma free days

An asthma-free or asthma-control day, as documented in each patient's diary, is a day during which there is

- no use of albuterol rescue (excluding the use of albuterol as pre-exercise treatment),
- no daytime or nighttime asthma symptoms,
- no peak expiratory flow of less than 80% of the predetermined reference value.

If any of the morning or evening records of rescue use, symptoms and peak flow are missing, that day is considered to be missing and is excluded from analysis.

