#### 6.5.2 RESCUE MEDICINE

Study sites provide inhaled rescue medication from our supplier to participants beginning at the Screening Visit and at every subsequent visit while the participant is in the study. Participants may use their personal rescue medication as needed as prescribed by their treating physician if they prefer it to the study supplied rescue medication.

- Rescue medications may include: albuterol, levalbuterol, ipratropium and albuterol/Ipratropium. Participants may not use ICS/LABA combination drugs for rescue – i.e. no SMART therapy.
- The use of rescue medications is allowable at any time during the study.
- The study will record the use of rescue medications.

---

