#### Other secondary efficacy assessments

1. FEV1, post-BD
2. FVC, pre-BD
3. Exacerbations, time to first (as defined in Section 6.5.3)
4. Symptom Free days (defined using diary/CompEx data)
5. Healthcare utilization
  - a. Asthma-specific ED visits
  - b. Asthma-specific hospital admissions
  - c. Asthma-specific ICU admissions
6. Asthma free days using the AsthmaNet definition

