3.5.3 Asthma Exacerbations

An asthma exacerbation in PrecISE is defined as a worsening of asthma requiring the use of a systemic corticosteroid (at least 3 days of treatment) to prevent a serious outcome (Protocol Section 6.5.3). This definition is consistent with recommendations from the National Institutes of Health (NIH) Outcomes

Workshop.⁵ Events meeting one or more of the following criteria will be recorded as asthma exacerbations during the study:

- All worsening asthma events in which systemic corticosteroids were initiated to prevent a serious outcome, including use of systemic corticosteroids in association with any form of healthcare provider encounter
- All asthma-specific emergency department or urgent care visits that involved treatment with systemic corticosteroids (defined as evaluation and treatment for <24 hours in an ED or urgent care center)
- All asthma-specific hospitalizations that involved treatment with systemic corticosteroids (defined as admission to an inpatient facility and/or evaluation and treatment in a healthcare facility for ≥24 hours) (also reported as a serious adverse event (SAE))
- All asthma-specific intensive care unit admissions or intubations (also reported as a serious adverse event)
- All asthma-related deaths (also reported as a serious adverse event)

For the purposes of this study, a course of oral systemic corticosteroids (OCS) is defined as any increase of at least 20 mg prednisone or double the daily maintenance dose for a minimum of 3 days. Note that a single depo-injectable dose of corticosteroids or oral dexamethasone will be considered equivalent to a 3-day course of OCS. If the maintenance dose is <5 mg, an increase must be both a doubling of that dose and at least a 5 mg increase (e.g., 2.5 mg would need to increase to at least 7.5 mg to count as a course).

Two courses of systemic corticosteroids must be separated by at least two weeks to count as two exacerbations. The two-week clock starts when the corticosteroid course for the first exacerbation ends.

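### As written, the asthma-free-day rule in SAP 3.3 can pass a day with non-albuterol rescue or a day inside a steroid course for an exacerbation, if symptoms are absent and PEF is adequate

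*SAP*

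**What the plan says.** SAP 3.3 lists asthma-free days among the other secondary efficacy assessments and scores them from the participant's diary. Three conditions must hold:

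- Rescue: "no use of albuterol rescue (excluding the use of albuterol as pre-exercise treatment").
- Symptoms: "no daytime or nighttime asthma symptoms".
- Peak flow: "no peak expiratory flow of less than 80% of the predetermined reference value".

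A missing-data rule follows: "If any of the morning or evening records of rescue use, symptoms and peak flow are missing, that day is considered to be missing", and it is left out of the analysis.

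Protocol 8.1 defines the endpoint only by citation: "Asthma free days using the AsthmaNet definition". SAP 7.5 analyses it with the MMRM used for the primary endpoints.

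Two other parts of the plan bear on the definition. Protocol 6.5.2 states: "Rescue medications may include: albuterol, levalbuterol, ipratropium and albuterol/Ipratropium", and lets participants keep their own rescue drug. SAP 3.5.3 defines an exacerbation as a "worsening of asthma requiring the use of a systemic corticosteroid (at least 3 days of treatment) to prevent a serious outcome".

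**The concern.** The conditions in SAP 3.3 are narrower than the trial's own account of rescue treatment and of exacerbations. The rescue condition names one drug where the protocol permits others. No condition refers to systemic corticosteroids, exacerbations or acute asthma care.

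The trial treats the steroid course as part of the exacerbation: under SAP 3.5.3 the two-week interval before a new event can count starts only when the course ends. One day can therefore lie inside a recorded exacerbation and also be scored asthma-free, once treatment has settled symptoms and restored peak flow.

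At stake is the meaning of one secondary endpoint and, if exacerbation rates differ between active and placebo periods, some of its ability to show that difference.

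**Working it through.** The plan gives no figure to reproduce. The check compares the definitions, then bounds the number of days exposed.

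**1. Rescue condition against permitted rescue drugs (SAP 3.3, Protocol 6.5.2)**

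| Permitted rescue | Fails the condition as worded? |
|---|---|
| Albuterol | Yes |
| Albuterol/ipratropium | Yes, it contains albuterol |
| Levalbuterol alone | No |
| Ipratropium alone | No |

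The diary item in SAP 3.2 is generic: "Reliever use morning/evening (doses"). The missing-day rule in SAP 3.3 likewise speaks of rescue use without naming a drug. The programmed variable may therefore already cover every reliever, but the SAP does not say so.

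**2. Steroid-course days: does any rule remove them?**

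- SAP 3.3: no steroid or exacerbation condition.
- Protocol 8.1: a citation only, with no components written out.
- Protocol 7.1.1: participants who respond to systemic steroids stay on treatment unless it is their third exacerbation in that period. Course days therefore fall inside analysed periods.
- SAP 3.5.4: removes only assessments made after a major change in therapy. Under Protocol 6.5.4, oral steroid use becomes a major change only when it runs beyond exacerbation treatment and is meant to continue.
- Protocol 9.5.2.1 and SAP 7.5: no exclusion added.
- SAP Table 2: exacerbations are intercurrent events for FEV1 and ACQ-6 and are built into CompEx. Asthma-free days have no entry.

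Nothing closes the gap.

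**3. Days exposed**

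Inputs: the recommended course in Protocol 6.5.3 is three days at the top dose, then five daily steps down, so 3 + 5 = 8 dosing days. A treatment period is 16 weeks, so 16 × 7 = 112 days. Treatment stops at three exacerbations in a period (Protocol 7.1.1), so two courses can occur with treatment continuing.

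- One course: 8/112 = 7.1% of the period.
- Two courses: 16/112 = 14.3%.

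These are ceilings for the recommended course, because a day must also pass the symptom, rescue and PEF conditions to be misclassified. Other course lengths are accepted. A 3-day course exposes 3/112 = 2.7%. The longest run that stays under the 21-day discontinuation rule in Protocol 7.1.1 is 20 days, or 20/112 = 17.9%.

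**4. Direction**

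Let *c* be courses per period, *d* days per course and *s* the share of course days that pass all three diary conditions. Days wrongly scored asthma-free per period are *c × d × s*. With *d* and *s* alike in both arms, the error in the active-minus-placebo difference is (*c* active − *c* placebo) × *d* × *s*. This is negative when the intervention lowers *c*, so it offsets part of a true benefit. The documents give neither *c* by arm nor *s*.

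**The case against.** The best defence has three parts.

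First, the rescue half may be wording only. The endpoint is scored from the diary, the only reliever variable described is generic, and rescue taken for symptoms would usually fail the symptom condition as well. This largely stands. A reader might infer that every levalbuterol or ipratropium rescue day passes; that would need drug-level diary data, which the documents do not describe. What remains is a mismatch between an albuterol-only condition and a generic variable.

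Second, this is a diary-state measure adopted by citation, and exacerbations are captured elsewhere by CompEx, time to first exacerbation and healthcare utilisation. It is true that no departure from the cited definition can be shown from these documents. But counting exacerbations in other endpoints does not make a day on an exacerbation course asthma-free, and the steroid half has no alternative reading.

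Third, the effect cannot be sized. This stands. A reader might assume 0.5 courses per period on placebo, 0.3 on drug and half of course days clear, and obtain (0.5 − 0.3) × 8 × 0.5 = 0.8 day per period, about 0.7% of 112 days. None of those three assumptions comes from the documents.

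**Conclusion.** The gap is real on the written text and minor in consequence. The steroid part is firm; the rescue part may need only a wording correction. Exposure is at most 7.1% of a treatment period per recommended course and 14.3% for two. The share actually misclassified is unknown.

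If an intervention reduces exacerbations, and course length and the clear share are similar in both arms, its effect on asthma-free days would be diluted relative to scoring those days as not asthma-free.

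A reader might go further and infer that the arm with more exacerbations comes out ahead, or that this endpoint will contradict CompEx. The documents do not support that. An exacerbation also costs asthma-free days through symptoms, rescue use and low PEF, all of which already fail the rule, and the net balance is not given. The primary endpoints and CompEx do not use this definition.

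**What to change.** In SAP 3.3:

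1. Replace the albuterol-only condition with: *no use of any rescue medication permitted in Protocol 6.5.2, pre-exercise use excepted*.
2. Add: *a day with a complete diary is scored not asthma-free if it falls within a systemic corticosteroid course for asthma (an increase over maintenance, as defined in 3.5.3), or within an asthma-specific ED, urgent care or hospital stay, using recorded start and stop dates*. Tying this to an increase keeps stable maintenance steroid from failing every day.
3. State a convention for single-dose courses, which SAP 3.5.3 equates to a 3-day course, and for dates known only to the month, which one accepted form of documentation in Protocol 6.5.3 allows.
4. Keep the existing missing-day rule in the main analysis. Overriding it only during exacerbations would treat incomplete days differently inside and outside events. Scoring incomplete-diary days within exacerbations as not asthma-free can be a sensitivity analysis.

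The cost is a short SAP edit, a merge with exacerbation and medication dates already collected, the date conventions, and a check that the text agrees with the definition cited in Protocol 8.1. Under SAP 1.4, blinded statisticians may still amend the SAP after an intervention's first unblinded review. The change affects scoring only, not patient care.

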3.4 Exploratory Efficacy Assessments

1. Rate of recovery from exacerbation, time to improvement after
2. Economic burden of disease assessment (Days missed from work/school, cost of hospitalizations)
3. Asthma Quality of Life Questionnaire (AQLQ)
4. Work Productivity and Activity Impairment Questionnaire (WPAI)⁴
5. Modified Asthma Severity Scoring System (ASSESS)

3.5 Study Definitions and Created Variables

3.5.1 Visits

- Baseline visit is Visit X.1, where X indicates the treatment period and ranges from 1 to 6.
- Endpoint visit is Visit X.5, where X indicates the treatment period and ranges from 1 to 6.
- On-treatment visits are monthly and include Visits X.2, X.3, X.4, and X.5
- Visit windows for baseline and on-treatment visits are ± 5 days

3.5.2 End of Study

The original timeline for randomization and study completion has been extended due to the impact of the Covid-19 pandemic. The last randomization visit is now expected to occur in February 2024 and the last on-treatment visit in December 2024. Safety follow-up will conclude in February 2025, 54 months after enrollment was resumed in August 2020 following the shut-down due to the Covid-19 pandemic. Study closeout, analyses and dissemination of findings will conclude in June 2025.

3.5.3 Asthma Exacerbations

An asthma exacerbation in PrecISE is defined as a worsening of asthma requiring the use of a systemic corticosteroid (at least 3 days of treatment) to prevent a serious outcome (Protocol Section 6.5.3). This definition is consistent with recommendations from the National Institutes of Health (NIH) Outcomes

Workshop.⁵ Events meeting one or more of the following criteria will be recorded as asthma exacerbations during the study:

- All worsening asthma events in which systemic corticosteroids were initiated to prevent a serious outcome, including use of systemic corticosteroids in association with any form of healthcare provider encounter
- All asthma-specific emergency department or urgent care visits that involved treatment with systemic corticosteroids (defined as evaluation and treatment for <24 hours in an ED or urgent care center)
- All asthma-specific hospitalizations that involved treatment with systemic corticosteroids (defined as admission to an inpatient facility and/or evaluation and treatment in a healthcare facility for ≥24 hours) (also reported as a serious adverse event (SAE))
- All asthma-specific intensive care unit admissions or intubations (also reported as a serious adverse event)
- All asthma-related deaths (also reported as a serious adverse event)

For the purposes of this study, a course of oral systemic corticosteroids (OCS) is defined as any increase of at least 20 mg prednisone or double the daily maintenance dose for a minimum of 3 days. Note that a single depo-injectable dose of corticosteroids or oral dexamethasone will be considered equivalent to a 3-day course of OCS. If the maintenance dose is <5 mg, an increase must be both a doubling of that dose and at least a 5 mg increase (e.g., 2.5 mg would need to increase to at least 7.5 mg to count as a course).

Two courses of systemic corticosteroids must be separated by at least two weeks to count as two exacerbations. The two-week clock starts when the corticosteroid course for the first exacerbation ends.

3.5.4 Major Change in Therapy

A major change in therapy is defined in Section 6.5.4 of the protocol. If a participant has a major change in therapy during a treatment period, they will discontinue their current assigned treatment and then discontinue the study. Any assessments collected after the major change in therapy will not be included in the efficacy analyses.

4. Randomization

4.1 Two-Step Randomization Procedure

Randomization and re-randomization are implemented in two steps throughout the study, as follows:

1. At the first step, participants eligible for the study are randomly assigned to receive one of the study interventions from among the set of interventions for which they are eligible, after applying intervention-specific exclusion criteria.
2. At the second step, participants are randomly assigned to receive test treatment or placebo with a method that depends on study phase:
 - a. 2-period crossover phase: participants beginning period 1 are assigned a crossover sequence (T:P or P:T) with equal probability, to achieve a 1:1 allocation of test treatment versus placebo in each of the 1st two periods.
 - b. Single-period crossover phase with repeated re-randomizations: Participants beginning period 3 and higher are assigned either test treatment or placebo with unequal probability, with the goal of 25% of all participants receiving a second placebo.

4.2 Intervention Assignment

Each of the five interventions has a target (biomarker positive) subgroup defined based on a priori information available at the time the intervention enters the trial (Table 1). Each participant's status relative to the target subgroups is based on the biomarker profile determined at screening.

The target subgroups initially defined for each intervention have some degree of overlap, such that participants may be in the target subgroup for more than one intervention. In this sense, the interventions are competing with each other for targeted participants. The 1st-step randomization probabilities are applied to determine which intervention a participant is assigned among those interventions for which they are eligible. These probabilities are adjusted throughout the study to ensure the study objectives can be met. That is, accrued data on intervention eligibility and biomarker profiles (target subgroup membership) are monitored during the study, and randomization probabilities adjusted as needed to ensure a sufficient number of treatment periods (test and placebo) are available to support the planned interim (futility) and final (efficacy and precision medicine) analyses.

The initial randomization algorithm, implemented at study start, was guided by the following principles, given in priority order:

1. Interventions that have not yet reached the required sample size to test for futility are favored over interventions that have already enrolled enough subjects to conduct the futility analysis.
2. Interventions are randomly assigned to favor participants in the target subgroup of an intervention over participants outside that subgroup in 2:1 ratio, until the time of the interim analysis for futility.
3. Intervention assignment takes into consideration the distribution of three prognostic factors for asthma outcomes: (i) past-year exacerbations at the study's baseline (assessed during the initial screening period), (ii) blood eosinophils, and (iii) IL-6 plasma levels. The goal is to ensure that participants contributing to the efficacy analysis (interim and final) of each intervention resemble the severe asthma subpopulation with respect to these three factors. Initial targets for balancing were based on the factor distributions in the SARP population of severe asthma patients and are updated as PrecISE baseline data become available.

Due to delays in certain interventions being available to enter the study in addition to the pandemic shut-down, modifications to the initial randomization algorithm are needed to achieve the target sample sizes for each intervention at interim and final analysis times. Simulations based on participant accrual, eligibility data, and biomarker profiles are conducted periodically during the study (by statisticians masked to treatment assignments and outcome data) to predict the treatment periods that will be available for each intervention and each analysis time point. Randomization probabilities for intervention assignment are then adjusted, as needed, to achieve the required sample sizes for these analyses.

